9.6.6 Premature Discontinuation of Study Drug Follow-up Telephone Contact Visit

Patients who prematurely discontinued study drug during the study, for reasons other than withdrawal of consent, will have completed TV14 and the Washout and Follow-up Safety Period Visit. These patients are to be contacted by telephone 30 days (+ 2 weeks) after the visit that the patient met the Failure-to-Improve criteria and stopped medication.

During this Telephone Contact, record AEs and changes in concomitant medications since the completion of the Washout and Follow-up Safety Period Visit.

Document any additional efforts that take place to reach a patient who is non-responsive to telephone contact.

9.6.7 Early Termination Visit for Patients who Withdraw Consent

Patients may withdraw consent from the study at any time. However, if feasible for the patient, the following procedures should take place as part of an Early Termination Visit:

- obtain vital signs
- perform physical examination
- complete the PAS
- perform brief neurological assessment
- collect blood for central laboratory (hematology and chemistry) and serum pregnancy test at the central laboratory
- collect blood for PK
- Perform 12-Lead ECG after at least 5 minutes in a supine position (See the Study Reference Manual for ECG procedures, [section 17.4](#) Electrocardiograms for the handling of Cardiovascular adverse events)
- collect urine for urinalysis at central lab
- administer PRO measurements:
 - Worst itch NRS
 - Average itch intensity NRS

- VRS
- ItchyQoL
- MOS Sleep-R
- HADS
- SOWS
- PBI-P

The PRO questionnaires must be administered at the study site under the supervision of and by trained study staff, strictly adhering to PRO Administration Instructions (see Study Reference Manual).

- record AEs
- review of concomitant medications, including over-the-counter medications, nutritional supplements, and vitamins
- perform study drug accountability, final retrieval of any dispensed study drug

9.6.8 Unscheduled Visits

If a patient needs to be evaluated in relation to the study on a day other than one of the study visit days, that day will be considered an Unscheduled Visit. The reason for each unscheduled visit will be recorded and the following procedures will be performed: vital signs (BP, HR, RR, temperature), assessment for AEs, review of concomitant medications (including rescue medications), and Study Drug accountability. Additional procedures such as central or local laboratory sample collection may also take place, if clinically indicated. All unscheduled visits will be recorded on the Unscheduled Visit CRF.

9.6.9 Schedule of Events

The Schedule of Events is shown in [Appendix 1](#) and is described in [Section 9.6](#).

9.7 STUDY DRUG TREATMENT AND DRUG ACCOUNTABILITY

Please see the Study Reference Manual for additional information on Study Drug supplies, packaging, storage, dispensation, and accountability.

9.7.1 Study Drug Dosing

Following enrollment, the patient will receive 30 mg open-label tablets. At each visit at which study drug is to be dispensed, enough study drug should be supplied to ensure a sufficient number of tablets until the next visit plus an additional 8 tablets to allow for visit windows and/or possibility of a missed visit. Bottles can be re-dispensed, as appropriate.

Study drug can be taken with or without food. Patients will be instructed to take the AM and PM Study Drug tablets at the same times of the day, approximately 12 hours apart, preferably with 240 mL (approximately 8 ounces) of water. If the patient does not take a particular dose at the planned time he or she may take it up to 2 hours later. For example, if a patient is taking the Study Drug at 9 AM and 9 PM but forgets to take the 9 AM dose, he may take the 9 AM dose as late as 11 AM. After that time, the patient should skip the 9 AM dose and, instead, take the regularly scheduled next dose at 9 PM.

The first dosing day will be on either Visit 1a or Visit 1b. Titration will be based on tolerability. If the patient is experiencing a study-drug related AE or an AE that may be

aggravated by study drug uptitration, the study drug dose should not be increased, regardless of the NRS score.

The Study Drug will be titrated during the Treatment Weeks 1 - 4, according to the schedule in [Table 3](#) to a final dose of 30 mg BID up to 180 mg BID. The dosing for Treatment Week 1 is further described in [Section 9.6.1](#) (Visit 1a) and [Section 9.6.4](#) (Visit 1b).

Patients will titrate to tolerability beginning with a 30 mg dose on Day 1 (Visit 1a or Visit 1b) with a dose increase of 30 mg BID not more often than every 3 to 4 days in order to attain steady-state plasma concentrations of nalbuphine at each dose.

The achieved dose attained as of the end of Treatment Week 4 will be maintained throughout the rest of the Treatment Period. This dose will be defined as the patient's "maintenance dose". A single dose reduction or dose hold per patient is permitted during Treatment Period at the investigator's discretion. If subsequent dose reductions or dose interruptions are needed, the Medical Monitor must be contacted. The duration of any dose hold must be discussed with the Medical Monitor.

Table 3: Dosing Schedule for TR03ext

Week of Treatment Period ¹ (TV or TC)	Day	Drug Tolerance		Discontinuation
		Acceptable	Unacceptable ³	
Week 1 (TV1/Visit1a /1b)	1	30 mg (PM dose)	--	
	2	0 mg (AM dose) 30 mg (PM dose)	--	
TC#1	3-4	30 mg BID		
	5-7	Titrate patients to tolerability with dose increases of 30 mg BID. Maintain dose for at least 3 to 4 days up to next dose level	Reduce dose incrementally by 30 mg	NA
The highest possible titration dose by the end of Treatment Week 1 is 60 mg BID				
Week 2 ²	1-7	Continue incremental increase in dose and maintaining at each dosed level for 3 to 4 days	Reduce dose incrementally by 30 mg	If 30 mg BID is not tolerated within one week, discontinue subject
The highest possible titration dose by the end of Treatment Week 2 is 120 mg BID				
Week 3 ²	1-7	Continue dose increase	Reduce dose by 30 mg BID and maintain	If 30 mg BID is not tolerated within one week, discontinue subject
The highest possible titration dose by the end of Treatment Week 3 is 180 mg BID				
Week 4 ² (TC#2)	1-7	Maintain dose at highest dose level reached on Week 3 Day 7	Reduce dose reached on Week 3 Day 7 by either 30 or 60 mg and maintain	NA
Treatment Week 5 ⁴ up to Treatment Week 50 (TV3-TV 14)	1-7	Maintain dose from Week 4 through TV14 ^{5,6}	Patient may down titrate twice over remaining duration of study	Patient discontinued if a 3 rd time down-titration is needed.

¹The decision to enter the patient into the Titration Period is based on Worst Itch NRS score NRS ≥ 5 obtained from the patient on Visit 1a or 1b

²The titration decision will be made based on tolerance to study drug

³Tolerance level is unacceptable to either the patient and/or investigator.

⁴The number of Treatment Weeks prior to TV 14 will vary for patients previously in the Observation Period depending upon the number of weeks spent in the Observation Period. See [Table 8](#)

⁵The achieved dose attained as of the end of Treatment Week 4 will be maintained throughout the rest of the Treatment Period. This dose will be defined as the patient's "maintenance dose". Two dose reductions to the next lower allowed dose are permitted during Treatment Weeks 5 – 50 (e.g., a patient at 90 mg BID can be reduced to 60 mg BID). If a third dose reduction is needed, the patient should be discontinued from the study.

⁶ Beginning on TV 3 and at every subsequent Treatment Visit, patients with a Worst itch NRS \geq the Worst itch NRS at Visit 1a (or at Visit 1b in the case of patient who require the OV period) will be discontinued from study drug, complete the End of Treatment Visit 14, the Washout and Safety Follow-up Period and Visit, and a Telephone Contact Visit 30 days after the last dose of study drug.

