9.6 STUDY PROCEDURES

Before the initiation of study-specific procedures the patient must be given a complete explanation of the purpose of the study, evaluations to be conducted, and risks/benefits for study participation. Patients must understand the requirements of the study, provide informed consent (See [Section 9.6.1](#) and [Section 20.3](#)), agree to the study restrictions, and agree to return for the required assessments. After review of the informed consent is documented, the patient must give witnessed verbal and written consent. For this study, patients will retain their study number from study TR03.

With the exception of Visits 1a and 1b, windows for all visits will be +/-3 Days. Please see the Schedule of Events in [Appendix 1](#) for details of the Titration Period assessments and the Study Schematics Flow Charts in [Appendix 2](#). See [Section 9.7.1](#) for details of Study Drug Dosing and [Section 9.7.6.4](#) for information on the use of pre-medications with the Study Drug. Visit 6 of TR03 will serve as TR03ext Visit 1a.

Visit 1a has procedures to be done as summarized in [Section 9.6.1](#) regardless of the patient's pruritus intensity score. Following a set of common procedures, only patients who qualify for the Treatment Period based on meeting the pruritus intensity criteria will be eligible to receive study drug; Visit 1a corresponds to TV1. For patients who, during the final visit of TR03, did not meet the pruritus intensity criteria to enter the TR03ext Treatment Period, Visit 1a corresponds to OV1, the first visit of the Observation Period. If during a subsequent observation period visit to the site, the patient meets the pruritus intensity criteria, then that observation visit immediately transitions into Visit 1b (it also corresponds to TV1 since it is now the first Treatment Period visit) – See [Section 9.6.3.3](#) and [Section 9.6.4](#).

For subjects who transition to the Treatment Period from the Observation Period, [Table 8](#) provides details on the treatment visit schedule based on the study week that the subject transitioned from the Observation Period to the Treatment Period. The subject will follow the Treatment Visit schedule outlined on the Schedule of Events ([Appendix 1](#)).

For clarity,

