9.6.2.1.2 TV 2 (Treatment Week 3)

The following procedures are to take place at this visit:

- obtain vital signs
- collect urine for pregnancy (must be confirmed negative prior to dispensing study drug)
- collect blood for PK
- perform 12-Lead ECG after at least 5 minutes in a supine position (See the Study Reference Manual for ECG procedures, [section 17.4](#) Electrocardiograms for the handling of Cardiovascular adverse events)
- perform brief neurological assessment
- administer PRO measurements:
 - Worst itch NRS
 - Average itch intensity NRS
 - VRS
 - ItchyQoL
 - MOS Sleep-R
 - HADS.

The PRO questionnaires must be administered at the study site under the supervision of and by trained study staff, strictly adhering to PRO Administration Instructions (see Study Reference Manual).

- record AEs (including tolerability to study drug)
- review concomitant medications, including over-the-counter medications, nutritional supplements, and vitamins
- reinforce compliance
- perform Study Drug accountability, retrieve previously dispensed Study Drug
- dispense the Study Drug to the patient required until return at TV3 (Treatment Week 5)
- Document tolerability/intolerability to study drug and titration decision based on [Table 3](#)
- Discontinue study medication in patients who could not tolerate 30 mg BID dose and complete the End of Treatment Visit, TV14 (See [Section 9.6.2.2.12](#) and [Section 11](#))

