9.6.2.2.1 TV 3 (Treatment Week 5)

The following procedures are to take place at this visit:

- Administer the Worst Itch NRS and evaluate against the Failure-to-Improve criteria (see [Section 11.1](#))
- For patients who MEET the Failure-to Improve criteria
 - Stop study medication
 - Perform End of Treatment Visit (TV14) procedures
- For patients who DO NOT meet Failure-to-Improve criteria, perform the following procedures
 - obtain vital signs
 - collect urine for pregnancy test (must be confirmed negative prior to dispensing study drug)
 - collect blood for PK
 - perform 12-Lead ECG after at least 5 minutes in a supine position (See the Study Reference Manual for ECG procedures, [section 17.4](#) Electrocardiograms for the handling of Cardiovascular adverse events)
 - perform brief neurological assessment
 - administer PRO measurements:
 - Average itch intensity NRS

- VRS
- ItchyQoL
- MOS Sleep-R
- HADS

The PRO questionnaires must be administered at the study site under the supervision of and by trained study staff, strictly adhering to PRO Administration Instructions (see Study Reference Manual).

- record AEs
- review of concomitant medications, including over-the-counter medications, nutritional supplements, and vitamins
- reinforce compliance
- perform study drug accountability, retrieve previously dispensed study drug
- dispense the study drug to the patient required until the next Treatment Visit

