9.7.3 Multiple Missed Doses

If a patient misses multiple doses of the Study Drug, please follow the procedures below. In no case should patients take additional doses of Study Drug to make up for missed doses. If Study Drug is re-started after missed doses, the patient should be instructed to take Study Drug from the tablets designated for the visit during which Study Drug is being re-started rather than from the visits during which Study Drug doses were missed.

- **During the Titration Period**

If a patient misses 3 (or more) consecutive doses, please contact the study Medical Monitor.

- **During the Stable Dose Period**

If a patient misses 6 (or more) consecutive doses, please contact the study Medical Monitor. If authorized by the Medical Monitor, patients who miss more than 6 consecutive doses may be allowed to continue on study. In such situations, patients should receive the Study Drug only once daily (i.e., the AM or PM dose only) for the first 3 days before returning to the full (BID) target dose.

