10.1 FORMULATION, PACKAGING AND LABELING

The Study Drug in this trial is nalbuphine HCl ER tablets. Nalbuphine HCl ER tablets are white to off white film-coated round tablet containing either 30 mg or 60 mg nalbuphine HCl.

All study medication will be supplied by the Sponsor. Following confirmation of eligibility to start the Treatment Period, the patient will receive bottles of study drug tablets containing 60 tablets each. Bottles will be labeled with at minimum: contents, storage conditions, expiration date, clinical trial statement, and the name and lot number of the study drug Sponsor (Trevi Therapeutics).

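### The flat 8-tablet overage covers the ±3-day visit window only at 30 mg BID, and covers a missed four-week visit at no dose

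*Protocol*

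**What the plan says.** Section 9.7.1 (Version 2.0) states that after enrolment "the patient will receive 30 mg open-label tablets", titrated "to a final dose of 30 mg BID up to 180 mg BID" in steps of 30 mg BID. Each dispensing must last "until the next visit plus an additional 8 tablets to allow for visit windows and/or possibility of a missed visit". The figure of 8 is not tied to dose, and no derivation is given.

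Section 9.6 sets the window: "With the exception of Visits 1a and 1b, windows for all visits will be +/-3 Days". Section 10.1 names both 30 mg and 60 mg tablets and says "the patient will receive bottles of study drug tablets containing 60 tablets each". Section 9.7.1 lets bottles be dispensed again.

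From TV3 (Section 9.6.2.2.1) each treatment visit opens with the instruction "Administer the Worst Itch NRS and evaluate against the Failure-to-Improve criteria". Under Table 3, footnote 6, a score at or above the entry value ends study drug. In the Stable Dose Period, Section 9.7.3 says: "If a patient misses 6 (or more) consecutive doses, please contact the study Medical Monitor".

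**The concern.** The overage has two stated purposes: the visit window and a missed visit. Daily tablet use varies sixfold across the permitted doses, so a fixed tablet count cannot give a fixed number of days. Where it falls short, a patient who attends late but within the protocol runs out of drug before the visit.

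This matters because of what happens at that visit. The Worst Itch NRS asks about the past 24 hours (Section 9.7.7.1), and a single score decides whether treatment continues. Section 9.2 justifies that rule by about two weeks on a stable dose. A supply gap undercuts that premise, and the score and the PK sample may reflect a patient who is partly or wholly off drug. A gap of 2 to 5 doses also stays below the 6-dose trigger for contacting the Medical Monitor in the stable period, although the Dosing Diary should show it.

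**Working it through.** **Inputs.** 30 mg tablets, an overage of 8, and doses of 30 to 180 mg BID in 30 mg steps (Section 9.7.1); a window of ±3 days (Section 9.6); bottles of 60 (Section 10.1); visit weeks from the headings in Section 9.6.2.2. TV3 to TV13 fall at weeks 5, 9, 13, 17, 21, 26, 30, 34, 38, 42 and 46. Nine of those ten intervals are 28 days; TV7 to TV8 is 35 days.

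**The 8 tablets alone.** Tablets per day = 2 × dose/30. Days covered = 8 ÷ tablets per day. Needed for a visit 3 days late = 3 × tablets per day. Whole doses in 8 tablets = 8 ÷ (dose/30), rounded down; doses missed = 6 minus that number, not below 0. Needed for a missed four-week visit = 28 × tablets per day.

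| Dose (mg BID) | Tablets/day | Days covered by 8 | Needed for 3 days | Doses missed of 6 | Needed for 28 days |
|---|---|---|---|---|---|
| 30 | 2 | 4.0 | 6 | 0 | 56 |
| 60 | 4 | 2.0 | 12 | 2 | 112 |
| 90 | 6 | 1.33 | 18 | 4 | 168 |
| 120 | 8 | 1.0 | 24 | 4 | 224 |
| 150 | 10 | 0.8 | 30 | 5 | 280 |
| 180 | 12 | 0.67 | 36 | 5 | 336 |

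Eight tablets meet the 3-day requirement only at 30 mg BID. They meet the 28-day requirement nowhere.

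**Whole bottles of 30 mg tablets.** The base supply plus 8 is rounded up to a multiple of 60. Spare days = (issued − base) ÷ tablets per day.

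| Dose (mg BID) | 28 days + 8 → issued | Spare days | Missed of 6 | 35 days + 8 → issued | Spare days | Missed of 6 |
|---|---|---|---|---|---|---|
| 30 | 64 → 120 | 32 | 0 | 78 → 120 | 25 | 0 |
| 60 | 120 → 120 | 2.0 | 2 | 148 → 180 | 10 | 0 |
| 90 | 176 → 180 | 2.0 | 2 | 218 → 240 | 5.0 | 0 |
| 120 | 232 → 240 | 2.0 | 2 | 288 → 300 | 2.5 | 1 |
| 150 | 288 → 300 | 2.0 | 2 | 358 → 360 | 1.0 | 4 |
| 180 | 344 → 360 | 2.0 | 2 | 428 → 480 | 5.0 | 0 |

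Over the usual 28-day interval, rounding up leaves 2.0 spare days at every dose from 60 to 180 mg BID, one day short of the window.

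**TV2 to TV3 (14 days), the run-up to the first stop decision.** For a patient supplied at a constant 120 mg BID, 14 × 8 + 8 = 120 tablets, exactly two bottles. That leaves 1.0 spare day, so 4 of 6 doses are missed if TV3 is 3 days late.

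**If 60 mg tablets are used where they fit.** Tablets per day become 2 at 60, 4 at 90 and 120, and 6 at 150 and 180 mg BID. Eight tablets, in the mix of strengths the dose needs, then last 4.0, 2.0 and 1.33 days respectively. Only 60 mg BID is added to the doses covered.

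**The case against.** The strongest reply is that dispensing detail sits partly elsewhere. Section 9.7 refers to the Study Reference Manual, and Section 9.6.3.3 refers to Table 8 for the weeks of drug to dispense to Visit 1b patients. Neither the manual nor the Version 2.0 Table 8 is in the text available. That limits what can be said about actual supply at a site, but nothing visible replaces the figure of 8.

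Bottle dispensing is arguably the more natural reading of Section 10.1. The large counts of 4 and 5 missed doses then disappear over 28 days; what remains is 2 doses, and only for a patient more than 2 days late. Whole bottles also leave 32 spare days at 30 mg BID, and at 60 mg BID if 60 mg tablets are used, which would cover even a missed visit. These points stand. That cover comes from bottle size, however, and the shortfall remains at the other doses.

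The TV2–TV3 example needs a patient supplied for a constant 120 mg BID; one supplied for a rise to 180 mg BID who stays at 120 would have a surplus. If a visit is booked late in advance, the base supply should already allow for it, so only unplanned lateness draws on the overage.

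Finally, Section 9.2 expects that the antipruritic effect may outlast dosing, so a gap of 1 to 2.3 days need not return itch to baseline. That is fair, and no number of wrongful stops is claimed.

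**Conclusion.** The concern holds. With the 30 mg tablets that Section 9.7.1 names, the overage fails both its stated purposes at every dose above 30 mg BID, and at 30 mg BID it meets only the window. For a visit 3 days late the gap is 1 day at 60 mg BID (3 − 2.0), rising to 2.33 days at 180 mg BID (3 − 0.67); with whole bottles over 28 days it is 1 day at each dose from 60 to 180 mg BID. After a missed four-week visit, the 8 tablets alone leave 24 days (28 − 4.0) to 27.3 days (28 − 0.67) without drug.

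These figures assume that base supply is counted to the scheduled visit, that lateness is unplanned, and that no leftover bottles are carried forward. Patients who attend early, on time or only slightly late have no gap. The effect is on exposure, on the itch score behind the stop rule and on PK, and its size in patients cannot be derived from the protocol. It should be corrected, but it does not undermine the trial.

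**What to change.** In Section 9.7.1, replace the 8 tablets with an overage of at least 3 days at the patient's current dose: 6, 12, 18, 24, 30 or 36 tablets of 30 mg at 30, 60, 90, 120, 150 or 180 mg BID. Delete the reference to a missed visit, or provide for that case separately, for example by an unscheduled resupply. Match the wording in the Study Reference Manual. No dose, dosing rule, visit or endpoint changes.

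The cost is one sentence and 4 to 28 more tablets per dispensing at 60 to 180 mg BID (12 − 8 to 36 − 8). If only whole bottles are issued, 28 days plus 3 days needs 62, 124, 186, 248, 310 or 372 tablets, rounded up to 120, 180, 240, 300, 360 or 420. That is one bottle more than now at each dose from 60 to 180 mg BID, and leftover bottles can already be dispensed again.
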